STUDY PROTOCOL

The Evaluation of The Effect of Routine Treatments Administrated in Pedodontics Clinics on Dental Anxiety in Children and Salivary Cortisol Levels

Study Identification

Unique Protocol ID: 2017-840

Brief Title: Dental Anxiety in Children and Salivary Cortisol Levels

Official Title: The Evaluation of The Effect of Routine Treatments Administrated in Pedodontics Clinics on Dental Anxiety in Children and Salivary Cortisol Levels

Document Date: February 20, 2019.

Study Population

The study was carried out following the approval by the local ethics committee (Malatya Clinical Studies Ethics Committee, 2017/76), and informed consent was signed by the parents. Power analysis was performed prior to the study in order to calculate the sample size. In the power analysis, for an $\alpha = 0.05$ and $1 - \beta$ (power) = 0.80, it was calculated that at least 12 patients is required per group. Therefore, the study was planned with 135 children with 15 children in each group. For that purpose 9 groups were formed as 6 restorative and 3 protective applications. The restorative treatment groups included procedures with- and without-local anesthesia (LA). Procedures with LA included the groups as root canal treatment, pulpotomy, two-surface restoration and one-surface restoration. Procedures without LA included the groups as two-surface restoration and one-surface restoration. The protective application groups included the groups as fluoride application (by disposable arch tray or by cotton roll) and fissure sealant.

Inclusion Criteria

A total of 135 children (69 females 51.1%, 66 males 49.9%), aged 7-8 years (7.37 ± 0.48 years), were admitted to Inonu University Faculty of Dentistry Department of Pediatric Dentistry. They were

apparently healthy and had no previous experience of dental treatment except oral diagnosis that took place 1-2 months ago. Children, who required at least one dental treatment in the upper right molar region, were included. As lower molar teeth region could differ in terms of infiltrative anesthesia block, we chose upper right molar teeth for sake of standardization.

Detailed intraoral and extraoral examination of the patients was performed by a single dentist (BA). The dentist carried out the procedures with the same colored uniform (wearing a blue uniform) in both sessions. The diagnosis and treatments were carried out by the same dentist. The personal, medical and dental history of the patients were obtained from their parents and recorded in the patients' files.

Frankl's Behaviours Rating Scale (FBRS) is a method that is frequently used in studies based on the rating of behaviours. Children's attitudes during the dental examination were evaluated using FBRS. Behaviours of the child are examined in four groups in FBRS: definitely negative (Frankl-1), negative (Frankl-2), positive (Frankl-3), and definitely positive (Frankl-4) ¹.

In terms of the standardization of the groups, only the children who were compatible with Frankl-3 or 4 classes were included in the study. Children with Frankl-1 and -2 classes had negative compliance to treatment and therefore they were not included in the study.

The patients were grouped according to treatment needs. The patients were divided into groups taking into consideration the requirements of having no pain, abscess, fistula and no need for dental treatment requiring urgent intervention. Patients, who did not meet the inclusion criteria for the study, who did not want to participate voluntarily, who ate and drank something 1 hour before the appointment, who used medication in the last 7 days, who used medication that may affect the salivary flow in the last 60 days or who left the dental treatment incomplete, were not included in the study.

Procedures Applied to Patients

Each patient who participated in the study was informed about the treatment to be applied to him/her and the measurements to be performed by using the tell-show-apply behavior method. Furthermore, the child informed the dentist about any discomforting stimuli by "raising his/her left hand up" and the dentist stopped when he/she received this warning.

In the groups treated with local anesthesia, banana or strawberry flavored topical anesthetic gel (Vision Dental Pat Gel, WP Dental, Germany) that children might like was applied first. Then, the local anesthetic solution [Ultracain D-S ampoule (40 mg articain + 0.012 mg epinephrine) Aventis Pharma, Istanbul, Turkey] was injected by the traditional method with the help of a 2 cc set inject plastic dental injector (Tibset Sterile Medical Equipment Industry Istanbul, Turkey). Only conventional root canal treatment and extirpation were planned for the children included in the root canal treatment group in the measurement session. In the groups to be treated with pulpotomy, it was noted that at least one of the approximal surfaces of the teeth had decay and iron sulfate (ViscoStat®, UltraDent, South Jordan, USA) was used as pulpotomy material. A Tofflemire matrix retainer and 0.05 mm thick matrix band (Hahnenkratt, Königsbach-Stein, Germany) were used in groups with a two-surface cavity. 2% NaF (Polimo® IMICRYL, Konya, Turkey) was preferred in groups who received fluoride application.

An aerator and micromotor were used as cavity preparation in the restorative treatment groups. Only the micromotor was used for polishing purposes in the protective treatment groups.

Study Design

The Facial Image Scale (FIS) comprises a row of five faces ranging from very happy to very unhappy and the children were asked to point at which face they felt most like at that moment ². FIS was assessed at three stages: at the moment they sat in the dental chair, 15 minutes after the start of the treatment, and 15 minutes after the end of the treatment. In the scoring of this scale, which consists of faces that express five different moods, the unhappiest face gets the score of 5 and the happiest face gets the score of 1. From the moment the patient sat in the dental chair, the probe of the bed-side monitor was attached to the patient's left index finger, and his/her heart rate and SpO₂ were monitored during the treatment period and the data were recorded. After the treatment of the patients was completed in that appointment, the CFSS-DS was filled in by the patients under the supervision of their parents. This scale consists of 15 questions about the different steps of dental treatment, such as injection, examination, dentist's use of rotary instruments, and the answers are scored from 1 (not

afraid at all) to 5 (very much afraid). Scoring shows a low level of anxiety between 15-31, a medium level of anxiety between 32-38, and a high level of anxiety at 39 and over.

In the mornings, 3 salivary samples were taken from the patients by their parents in the home environment, i.e. one day before the treatment, on the day of treatment and one day after the treatment. The non-stimulated total saliva was collected from the patients. The parents were warned about the fact that all of the three salivary samples should be taken at the 30th minute after awakening, between 07:00 and 07:30 am. Eating, drinking, brushing the teeth and using dental care products were not allowed. It was stated that they could store them in the cooler part of the refrigerator at +4 °C until the day of delivery to the dentist. For saliva collection, three labelled polypropylene tubes were given to the parents inside a sterile collection container. During the treatment period in the clinic, salivary samples were taken between 09.00 and 11.00 am. Saliva samples were taken in 3 stages, i.e. at the beginning of the treatment, at the 15th minute of the treatment, and 15 minutes after the end of the treatment. Sampling at 15th minute of the treatment process was standardized to correspond to the cavity with an aerator (at the enamel level) in restorative treatment groups and to the stage of polishing procedure with a micro motor in protective treatment groups. These measures were taken to prevent the saliva from contaminating the cavity. In the groups treated with local anesthesia, care was taken not to include blood in the samples. If there was a visible plaque in the protective treatment groups, it was removed with a sponge, and the sample was taken after the polishing procedure.

Six samples were taken from each of 135 patients, a total of 810 samples were obtained, and samples were kept at -70 °C until the day of analysis. The frozen samples were thawed at room temperature on the day of analysis and centrifuged at 3000 rpm for 5 minutes. Cortisol concentrations were measured by the ELISA (Enzyme-Linked Immunosorbent Assay) method in a microplate optical reader (Biotek, Synergy HT, USA) and quantified with its special software (Gen 5, Biotek, Synergy HT, USA) as reported by Ozgocer et al.^{3,4}.

1. Frankl S. Should the parent remain with the child in the dental operatory? *J. Dent. Child* 29: 150-163, 1962.

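### Leaving treatment incomplete is written as an eligibility exclusion, but it is known only after treatment starts and may be tied to the distress being measured (low severity)

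*Protocol*

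**What the plan says.** - **The clause (Protocol, Inclusion Criteria).** One sentence lists who was kept out: children not meeting the inclusion criteria, those unwilling, those who had recently eaten or drunk, those on certain medication, and those "who left the dental treatment incomplete, were not included in the study".
- **Dental history (Inclusion Criteria).** The children "had no previous experience of dental treatment except oral diagnosis that took place 1-2 months ago".
- **Screening (Inclusion Criteria).** Only Frankl classes 3 and 4 were admitted, and the children's "attitudes during the dental examination were evaluated using FBRS". Grouping also required "having no pain, abscess, fistula and no need for dental treatment requiring urgent intervention".
- **Hand signal (Procedures Applied to Patients).** A child could signal discomfort, and "the dentist stopped when he/she received this warning". The text does not say whether treatment then resumed, or whether a stop that ended the session counted as incomplete.
- **Timing of measures (Study Design).** Clinic saliva was taken "at the beginning of the treatment, at the 15th minute of the treatment, and 15 minutes after the end of the treatment", and FIS follows a similar three-stage pattern. "After the treatment of the patients was completed in that appointment, the CFSS-DS was filled in by the patients".
- **Numbers (Study Population).** "the study was planned with 135 children with 15 children in each group". The document then describes 135 children and 810 saliva samples.

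**The concern.** Every other item in the sentence can be checked before treatment begins. Leaving treatment incomplete cannot, so the clause removes children because of something that happens after treatment starts, while reading as an entry criterion.

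This matters because the outcomes are measures of distress and distress is a plausible reason to leave. If such children were dropped, the means of FIS, heart rate, clinic cortisol and CFSS-DS among those who remain may be too low. Groups were formed by treatment need and run from root canal treatment under local anaesthesia to fluoride application. If leaving was more frequent in the more invasive groups, their contrasts with the others may shrink. If nobody left, or leaving had nothing to do with distress, there is no bias. Equal loss with the same link to distress leaves the contrasts unaffected.

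**Working it through.** **1. Which treatment does the clause mean?** Enrolled children had no earlier dental treatment beyond a diagnostic visit, so an earlier abandoned treatment is ruled out. The clause refers to the study treatment. The text does not settle whether that is the measured appointment or the whole course: Inclusion Criteria mentions two sessions, and Procedures Applied to Patients limits what was planned for the root canal group in the measured one.

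**2. Do the counts settle it?** 9 groups × 15 = 135, and 135 × 6 samples = 810, both as stated. Every child described gave all six samples. This fits no leavers, and it equally fits leavers who were replaced.

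**3. How large could the shift be?** The protocol gives no number of leavers and no link between leaving and outcome, so every input here is assumed. Let leaving be the top fraction p of a latent normal tendency that has correlation ρ with the outcome. The mean of those kept then falls by

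ρ × φ(z) / (1 − p), in SD units, where z is the 1 − p normal quantile.

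Example: p = 0.10 gives z = 1.28 and φ(z) = 0.1755; 0.1755 / 0.90 = 0.195; with ρ = 0.5 the fall is 0.097 SD. For scale, the standard error of a 15 v 15 difference is √(2/15) = 0.365 SD.

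| Loss in one group | φ(z)/(1 − p) | Fall in SD, ρ = 0.3 / 0.5 / 0.7 | Fall ÷ 0.365 |
|---|---|---|---|
| 2% | 0.049 | 0.015 / 0.025 / 0.035 | 0.04 / 0.07 / 0.09 |
| 5% | 0.109 | 0.033 / 0.054 / 0.076 | 0.09 / 0.15 / 0.21 |
| 10% | 0.195 | 0.058 / 0.097 / 0.136 | 0.16 / 0.27 / 0.37 |
| 20% | 0.350 | 0.105 / 0.175 / 0.245 | 0.29 / 0.48 / 0.67 |

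(Products are taken from unrounded values.)

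**4. In whole children.** With 15 kept, simulating the mean of the lowest 15 of 15 + k normal draws and multiplying by ρ = 0.3 to 0.7 gives:
- 1 leaver of 16 starters: 0.035 to 0.082 SD (0.10 to 0.22 standard errors)
- 2 of 17: 0.062 to 0.145 SD
- 3 of 18: 0.085 to 0.198 SD
- 4 of 19: 0.104 to 0.243 SD

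**5. Loss in both groups.** The contrast shrinks by ρ times the difference of the two factors.
- 20% v 10%: 0.350 − 0.195 = 0.155, so 0.05 to 0.11 SD.
- 10% v 5%: 0.195 − 0.109 = 0.086, so 0.03 to 0.06 SD.
- Equal loss with the same ρ: 0.

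**6. Cross-check with a second model.** If m leavers differ from 15 completers by D SD, the completers' mean differs from the starters' mean by −m/(15 + m) × D. For D = 0.5 to 1.5, one leaver gives 0.03 to 0.09 SD and three give 0.08 to 0.25 SD, the same scale as above. Five leavers at D = 1.5 give 5/20 × 1.5 = 0.375 SD, just over one standard error. Under the model in step 3, where the factor at 25% loss is 0.424, that would need ρ = 0.375/0.424 = 0.88, well outside the range used.

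**7. Scale against the design.** The 12 per group cannot be reproduced, since no effect size, SD or test is given, and the point does not rest on it. If it came from a two-sided two-group t-test (an assumption), the detectable difference is 1.20 SD. The 10%, ρ = 0.5 case is 0.097/1.20, about 8% of that.

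**The case against.** The case for leaving the text alone is substantial.

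- **Leaving was probably rare.** The children were cooperative at examination, free of pain and urgent need, willing, prepared by tell-show-apply, and able to halt the dentist. This stands as to frequency. But the Frankl rating came from the examination, before any injection or drilling, so it does not exclude distress that arises during treatment.
- **A completer population is defensible.** CFSS-DS and the last clinic stages exist only once treatment has ended. This stands, but the protocol presents the restriction as eligibility and does not say that results apply to completers.
- **Counts of starters and leavers belong in a results report.** This stands. Their absence is noticeable in a document written in the past tense with final numbers, but it is reporting detail and not an error by itself.
- **Incomplete may mean not returning for a later session.** This also stands. Such children would already have their clinic measures, which changes what is lost and how leaving relates to distress in the chair. The repair must therefore not presume one meaning.

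A reader might infer that a raised hand led to exclusion. The document says only that the dentist stopped, not that any session ended or any child was removed. A reader might also take the exact match of 135 planned and 135 described as a sign of replacement, but it fits zero leavers just as well.

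**Conclusion.** The point holds at low severity. The protocol states as eligibility a rule that acts after treatment starts, on an event plausibly related to the outcomes.

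The stronger reading, that the reported means *are* too low, is not supported. It would require that children left, that they left because of distress, and that each outcome is positively related to leaving. The document shows none of these. For the home morning sample taken the day before treatment, the link is more remote than for the clinic measures.

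The size is unknown and is zero if nobody left. In the illustrative cases with up to 20% loss and correlations of 0.3 to 0.7, it stays below one standard error of a 15 v 15 difference. Those figures show scale only and are not an estimate.

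**What to change.** 1. Remove the clause from the eligibility list and write it as a rule on non-completion. The rule should say whether incomplete refers to the measured appointment or to the whole course of treatment, and whether a stop after the hand signal that ends the session counts.
2. Keep eligible children who started treatment in their treatment-need group, with whatever FIS, heart-rate, SpO2 and saliva data were collected. Show completers only as a sensitivity analysis. Model details can stay with the SAP.
3. State that results apply to completers for measures that exist only after completion (CFSS-DS, post-treatment FIS and post-treatment clinic saliva), and for all measures if leavers' data were not kept.

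Items 1 and 3 are wording only. Item 2 needs records of who started and stopped, and the document does not say that these were kept. If they were not, say so and rely on item 3. No new patients, visits or samples are needed. The downside is that some children will have incomplete data. If incomplete refers to the measured appointment, item 2 recovers mainly what was measured before the child stopped, so the bias is reduced rather than removed.
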